To address this gap, we propose to develop an intervention that specifically targets fatigue and associated psychosocial symptoms. Bounce Back Now (BBN)¹³, an existing technology-enhanced, self-management mHealth intervention designed to address disaster survivors' psychosocial health needs using a smartphone-formatted approach, will be tailored and adapted for caregivers of children with food allergy(ies), hence the renaming to **Food Allergy Symptom Self-Management with Technology (FASST)** for caregivers. Over the course of 6-months, we will conduct preliminary feasibility testing of FASST in a 4-week small randomized trial of 30 caregivers of children \leq 18 years-of-age who are newly diagnosed (\leq 90 days from diagnosis) with food allergy(ies).

Aim 1a: Perform key informant interviews (n = 10) and analyze via conventional content analysis to determine ways to improve app acceptability.

Aim 1b: Adapt FASST using data collected during key informant interviews.

Aim 2: Conduct preliminary testing of implementation processes including feasibility, acceptability, adherence and satisfaction using the RE-AIM framework with process measures, surveys, and key informant interviews in 30 caregivers randomized to receive FASST (n = 20) or the control condition (i.e., basic app with resource links) (n = 10).

Aim 3: Obtain estimates of variability and measure caregiver experienced fatigue, anxiety, depression, sleep, self-efficacy, and quality of life at baseline, 4-week intervention completion and 3-months post intervention.

B. Significance

B1. Food allergy is a highly complex condition and is growing in frequency and severity among children, negatively affecting quality of life.

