The intervention will be a multicomponent (3-part) technology-based package delivered via a mobile device and used over a 4-week period. The intervention will target influences and processes informed by the Caregiving Process Model. **Component 1** (education and support) will consist of continuous access to directed educational resources about food allergy and its management. These materials will be easily accessible via a mobile device and will include embedded PDFs and links to websites developed and tested by authoritative sources. An example includes education materials provided by the Food Allergy Education and Research (FARE), the leading national organization and most trusted source of food allergy information, programs and resources, such as the Food Allergy & Anaphylaxis Emergency Care Plan. To address potential literacy barriers, all resources will be provided in a web compatible format and compliant with current accessibility guidelines. **Component 2** (symptom monitoring and tracking) will consist of a mobile-device based application for daily tracking and monitoring of fatigue, anxiety and other psychosocial symptoms in caregivers of children with newly diagnosed food allergy(ies) that also permits upload of physical and emotional symptom logs to study personnel. The PI or RA will send a daily text reminder to participants randomized to the intervention arm of the study reminding them to complete their daily physical and emotional symptom log. Logged symptom trends will be graphically illustrated by the application for participant viewing. Based on feedback from component 2, participants will be given directed guidance related to component 3 (symptom self-management). **Component 3** will consist of symptom-based interventions participants can utilize real-time. For example, if a participant logs symptoms related to anxiety, the application will recommend a brief guided intervention for relaxation, such as meditation, or deep breathing. If a participant logs symptoms related to fatigue, the application will recommend the participant listen to a short audio clip that offers ideas for achieving better sleep or suggestions for good sleep hygiene. We will collect data via the app on the frequency and patterns of usage and will also collect measures data for Aim 3 at baseline, 4-weeks intervention completion and 3-months post-intervention completion. As well, the RA will send caregivers a weekly text message using a semi-structured protocol to “check in” with participants and promote engagement.

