
D3.3. Control group

The control group will receive Component 1 of the intervention.

D3.4. Primary Aim 1a and 1b: Key informant interviews and intervention tailoring and adaptation

We will use a purposive sampling strategy to identify caregivers of children with established (≥ 1 year from diagnosis) food allergy(ies) familiar with the disease process and management. Data obtained through key informant interviews using a semi-structured protocol and a qualitative descriptive approach²¹ will inform tailoring and adaptation of FASST. The purpose of interviews will be to obtain feedback from caregivers of children with established food allergy(ies) who have been managing the condition for one year or more. Participants will be asked about their experience in the first year of managing their child’s food allergy, with specific questions regarding the first 4 weeks of management and the perceived impact on their psychosocial well-being and overall quality of life. Participants will be shown a mocked-up application on a mobile device and asked to provide feedback related to the content. At the beginning of the session, the PI will deliver detailed verbal instructions regarding use of the device and intervention components. Participants will be provided with mobile devices that have been prepared for the feasibility testing (Aim 2) with access to the FASST application and text messaging. After allowing time for participants to explore the intervention (with direct observation), the PI will ask 8-10 open-ended questions with probes using an interview guide. Questions will be designed to assess the acceptability, feasibility, and usability of the intervention. The interview will conclude with questions regarding suggested improvements to the intervention. The hands-on, observational session is expected to last 45 to 60 minutes and the interview is expected to last an additional 45 to 60 minutes. The PI will video record observations to inform adaptation of the intervention. The interview will be audio recorded and transcribed. Following data analysis (described in **D3.7.**) the results from the interviews will be used to adapt the intervention to meet the specific needs of caregivers of children ≤ 18 years-of-age with a newly diagnosed food allergy(ies).

D3.5. Primary Aim 2: Feasibility Testing

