To determine feasibility, we will apply the RE-AIM framework to assess the Reach, Efficacy, Adoption, Implementation, and Maintenance of the intervention with 30 caregivers.²² The domains are further explicated in Table 1. Participants will be asked to download the FASST app onto their mobile device with intervention components 1, 2, and 3 if randomized to the intervention arm and only component 1 if randomized to the control arm. The PI or RA will deliver detailed verbal instructions to the participants in both arms of the study on the use of the application and the respective intervention components. Participants will also receive written instructions and a contact number for technical assistance if needed. Baseline measures (Table 1) will be collected during the same meeting. Participants will participate in the intervention over a 4-week-period. At the end of the 4-week period, the PI will attend a post-intervention meeting with each individual caregiver participant during which measures data for Aim 3 will be collected. The PI will also collect frequency and patterns of usage data 3 months post-intervention to assess implementation and preliminary evidence of maintenance (Table 1). The PI will meet with the RA weekly during the intervention.

Post-intervention interviews. Five participants from each study arm will be randomly selected and asked to participate in post-intervention key informant interviews with the PI to obtain more in-depth data on accessibility, usability, and adherence to intervention guided by the RE-AIM framework (Table 1). Semi-structured interviews will be conducted in-person or via phone (participant's choice) using a qualitative descriptive approach,²¹ will last approximately 45-60 minutes, and will be conducted according to an interview guide with open-ended questions and probes.

Reimbursement for participants will be a \$50 gift card provided at each of the 3 data collection points, with participants in key informant interviews (pre- and post-intervention) receiving an additional \$50 gift card.

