Measures. Caregivers will complete self-report measures at baseline, 4-week intervention completion, and 3 months post-intervention. Self-report measures will be collected during meetings between the PI and the participant. Participants will complete measures using a mobile tablet device. Data will be captured using REDCap data management system. The PI will be present to answer questions but will be unobtrusive while measures are completed.

Table 1: Intervention Domains and Measures

Major tasks and domains	Measures/instruments/questions and Cronbach's alpha ()	Data sources and time points
Demographics/clinical characteristics	Caregiver demographics including age, marital status, employment status, race/ethnicity, highest education level, and income; child age, health history, race/ethnicity, medications, health care utilization, rural/urban residence, insurance, family characteristics	Caregiver interview; baseline
Reach: Sample Recruitment	Monitoring of sample representativeness; types of recruitment activities; rates of recruitment; % eligible, consented, provided with informational session	Recruitment tracking forms; quality checks by PI; weekly meetings with mentor, clinic staff, and research team
Efficacy: Fatigue Emotional distress: anxiety Emotional distress: depressive symptoms Quality of Life Sleep Disturbance Self-Efficacy	PROMIS Fatigue SF 6a(>0.9) ²³ PROMIS Emotional Distress: Anxiety 6a (0.97) ²⁴ PROMIS Emotional Distress: Depressive symptoms SF 6a (0.97) ²⁵ Food Allergy Quality of Life-Parental Burden (>0.85) ²⁶ PROMIS Sleep Disturbance SF 6a (0.9) ²⁷ Food Allergy Self-Efficacy Scale for Parents (0.63-0.89) ²⁸	Tracking forms; fidelity checklist; transmissions from web-based application to PI/RA; post-intervention interviews; weekly meeting with mentor, clinic staff, and research team; baseline, 4-weeks post-intervention, 3-months post-intervention
Measures of self-management behaviors:	# days recorded symptoms; # days and types of recorded treatments/interventions	

Monitoring and tracking symptoms		
Adoption: Adherence	# days symptoms recorded; # times problem-based intervention accessed; length of time in minutes problem-based intervention accessed; # times educational component accessed; length of time in minutes educational component accessed	Tracking forms; data transmitted from web-based application; fidelity checklist; weekly meetings with mentor and research team; caregiver interview at end of study

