Feasibility processes (Aim 2): For the feasibility trial, we will collect multiple measures informed by the RE-AIM framework to assess feasibility and inform future efficacy and effectiveness trials. Variables will include those pertaining to the study procedures as well as participant variables. Data to be collected are described in Table 1. Specifically, 95% confidence intervals for proportions will be used to estimate dichotomous outcomes including the proportion of caregivers who agree to participate out of the number approached, the proportion adherent to the intervention protocol, i.e. providing daily symptom monitoring/tracking, using the education component, etc. For the continuous feasibility measures (e.g., patient satisfaction scores from patient surveys and end-of-study interview), frequency distributions and the median and mean responses (with 95% confidence intervals) will be obtained.

Outcome measures and estimates of variability (Aim 3): Demographic and clinical variables obtained at baseline will be described via measures of central tendency (mean, median), variability and frequency distributions as appropriate. Additionally, demographic and clinical characteristics for those who adhered to the study protocol (study completers) versus those who did not adhere (non-adherers and drop-outs) will be compared to better describe the population for this study. For continuous measures for the caregiver (fatigue, anxiety, depression, quality of life, sleep disturbance, pain and self-efficacy), the difference between pre and post intervention measurements will be estimated via 95% confidence intervals.

Post-intervention qualitative analyses (Aim 2): Data collected from post-intervention key informant interviews will be analyzed using directed content analysis³⁰ and nVivo qualitative data analysis software version 10.³¹ Consistent with the directed content analysis approach, initial coding categories are identified according to the guiding theoretical model, and for this study, will reflect the RE-AIM domains.

D3.8. Timeline

Activity	Y1Q1	Y1Q2	Y1Q3	Y1Q4	Y2Q1	Y2Q2
Organization, IRB approval						
Adaptation of BBN to FASST						
Interviews with caregivers and providers						
Analysis of interview data						
Tailoring of FASST						
Recruitment						
Intervention delivery (with assessments)						
3-month follow up assessments						
Data analysis, manuscript preparation, grant submission						

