- Tracking and follow-up of participant accrual (inc. withdrawn consents) will minimize risk by identifying, disclosing, and mitigating any potentially unknown risk(s) of harm to study participants.
- Timely and appropriate reporting of informed consent process deficiencies, protocol deviations, privacy breaches, conflicts of interest, and/or changes in personnel.
- Ongoing soliciting, monitoring and appropriate reporting of adverse event activities.
- Timely and appropriate IRB submission of safety-related documents such as audit reports, sponsor progress reports, SMC reports, and other materials or communications that might impact the safe conduct of this study.
- Active cooperation with the IRB, ACO, sponsor, and other applicable entities in the event of a random or for-cause internal or external audit.

Institution-Wide Assurances

This protocol will be conducted fully in keeping with the signed MUSC IRB Principal Investigator Statement of Assurance and Department Chair's Statement of Assurance, when submitted to the IRB as a required component of the MUSC IRB Human Research Review Application.

3. Protecting Confidentiality of Participant Data

Certificate of Confidentiality. This study will be conducted in accordance with recently enacted policy regarding the automatic granting of Certificates of Confidentiality to NIH/NINR federally funded research. Participants will be made aware of their rights and the limitations of the release of Protected Health Information during the Informed Consent process.

Participant Screening and Enrollment. All data from participants screened for the study will be entered into an electronic study database. Designated research staff will collect, gather, and enter required data (written informed consent, HIPAA Authorization, and demographics) onto study data forms. Screened patients who do not meet study eligibility will have specific screening data entered into the study database. The collected data will be helpful in examining the patient population and feasibility of enrollment criteria and will include reason for exclusion. All dates will be shifted and other Personal Health Information (PHI) will be removed from the study database upon study completion. All data obtained from this study will be used for research purposes only and will comply with Federal HIPAA regulations. Master Screening and Enrollment Logs will be used by the PM to prepare reports on accrual and attrition for the PI and SMC.

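### Does the adherence proportion in D3.7 need a numerical cut-off written into the plan?

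*Combined protocol and SAP*

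**What the plan says.** Aim 2, under Specific Aims, is to "Conduct preliminary testing of implementation processes including feasibility, acceptability, adherence and satisfaction using the RE-AIM framework", so adherence is a named outcome of that aim. D3.7 (Feasibility processes, Aim 2) places it among the dichotomous outcomes to be estimated with 95% confidence intervals: "the proportion adherent to the intervention protocol, i.e. providing daily symptom monitoring/tracking, using the education component, etc". The same paragraph promises frequency distributions, means and medians for the continuous feasibility measures.

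The adherence row of Table 1 (under Adoption) lists "days symptoms recorded; # times problem-based intervention accessed; length of time in minutes problem-based intervention accessed", followed by the matching counts and minutes for the educational component. It has no cut-off.

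D3.2 describes a "technology-based package delivered via a mobile device and used over a 4-week period" and sends the daily logging reminder to the intervention arm only. D3.3 adds: "The control group will receive Component 1 of the intervention". On later use, D3.5 says: "The PI will also collect frequency and patterns of usage data 3 months post-intervention to assess implementation and preliminary evidence of maintenance".

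For Aim 3, D3.7 compares baseline characteristics of "those who adhered to the study protocol (study completers) versus those who did not adhere (non-adherers and drop-outs"). Section B.3 provides for attrition reporting: "Master Screening and Enrollment Logs will be used by the PM to prepare reports on accrual and attrition for the PI and SMC".

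**The concern.** A dichotomous outcome needs a rule that classifies each caregiver as yes or no. D3.7 gives an illustration that ends in an open list, and Table 1 gives only raw quantities. If the rule is chosen after the logs are seen, the reported proportion could reflect that choice as much as caregiver behaviour, and its confidence interval would not show this. D3.7 intends these measures to inform later trials, so a misleading adherence figure could be carried forward.

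The Aim 3 wording adds a second doubt. It treats adherers as the study completers, yet the opposing group names non-adherers separately from drop-outs. A caregiver who attends every visit but seldom opens the app could be put in either group.

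**Working it through.** **The plan's own figure.** There is none to reproduce. The documents state no adherence cut-off, target rate or interval width, and the sample-size section justifies N = 30 by pilot status alone.

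**Inputs from the documents.** The intervention lasts 4 weeks (D3.2), so 4 x 7 = 28 days. The FASST arm has 20 caregivers and the control arm 10 (Specific Aims).

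**Assumptions.** The documents give no logging rates. Days logged are taken as beta-binomial with n = 28, mean m and between-person correlation rho, where s = 1/rho - 1, a = m x s and b = (1 - m) x s.

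**Central case.** With m = 0.7 and rho = 0.3, s = 2.333, a = 1.633 and b = 0.7.

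| Rule | Probability adherent | Expected of 20 | Nearest count | Wilson 95% CI |
|---|---|---|---|---|
| 28 of 28 | 0.124 | 2.5 | 2 | 3-30% |
| at least 23 | 0.449 | 9.0 | 9 | 26-66% |
| at least 20 | 0.582 | 11.6 | 12 | 39-78% |
| at least 14 | 0.781 | 15.6 | 16 | 58-92% |

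**Yardstick.** The Wilson interval is widest at 10/20: 29.9% to 70.1%, a half-width of 20.1 points.

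**Range.** The grid is m = 0.5, 0.6, 0.7, 0.8, 0.9 crossed with rho = 0.2, 0.3, 0.4, 0.5, giving 20 scenarios. Each difference is P(at least the looser cut) minus P(at least the stricter cut).

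| Pair of cuts (days) | Difference, points | Scenarios above 20.1 |
|---|---|---|
| 28 v 14 | 26-76 | 20 of 20 |
| 28 v 20 | 20.5-59 | 20 of 20 |
| 28 v 23 | 11-44 | 15 of 20 |
| 23 v 14 | 9-46 | 13 of 20 |
| 20 v 14 | 5-30 | 5 of 20 |
| 23 v 20 | 4-17.5 | 0 of 20 |

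**Check with independent days.** At a daily logging probability of 0.90, 28/28 has probability 0.90^28 = 5.2%, about 1 of 20 (exact 95% CI 0.1-24.9%). At least 23 of 28 has probability 94.5%, about 19 of 20 (75.1-99.9%). Independence exaggerates the contrast, but it too comes from the perfect-logging rule.

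So the choice of rule matters most when every-day logging is one of the options. Between neighbouring tolerances it is smaller than the sampling error.

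**Arm and window.** Controls receive Component 1 only and have no symptom log, so the tracking denominator is the 20 FASST caregivers. Three-month usage is assigned in D3.5 to implementation and maintenance, whereas Table 1 places adherence under Adoption. The natural window is therefore the 4-week period, although the Table 1 row does not print one.

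**Aim 3 split.** Withdrawal of Subjects lets the PI withdraw participants who do not follow instructions, separately from those who leave by choice. Non-adherers and drop-outs can therefore mean PI-withdrawn plus self-withdrawn, set against completers. On that reading a low-use visit completer is simply a completer. The withdrawal rule is discretionary, so it makes this reading available without settling the wording. The number of caregivers affected cannot be estimated, because the documents give neither retention nor logging rates.

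**The case for a change.** The strongest case for a change is that D3.7 itself calls this outcome dichotomous and attaches a confidence interval. One sentence fixing the cut before the logs are opened would cost almost nothing. After-the-fact choice is also a practical possibility: Section F (Interim Analysis) has the PI and biostatistician producing semi-annual reports and evaluating adherence, so those who would set the cut may see the data first. Reading the text as one proportion per component still leaves tracking without a tolerance.

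Much of this stands. No numerical tolerance is written anywhere, the list of components is open-ended, and a pre-stated cut would be tidier.

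It does not amount to an unusable rule. Logging every day and using the education component at all can both be applied as written. Any particular looser cut, such as 20 of 28 days, would be a matter of preference with no source in the documents. Taking non-adherers out of the Aim 3 comparison would remove a group the investigators chose to describe. Freedom to choose the cut is also limited in effect, because the days-logged counts are collected and D3.7 plans distributions for continuous feasibility measures. If those counts are reported, a reader can apply any cut.

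**Conclusion.** No change to the plan follows. This is missing detail in the definition of one descriptive proportion and loose wording in one descriptive comparison. The sample-size section rules out hypothesis testing, and no progression criterion or sample size uses the adherence figure.

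The possible effect on that figure is large only when literal 28-of-28 logging is set against a clearly looser cut: about 20 to 76 points against 20 or 14 days. For 23 against 20 days it is 4 to 17.5 points, below the 20-point half-width at n = 20. These sizes rest on assumed logging means of 50-90% and correlations of 0.2-0.5. The dependence on the rule does not rest on any single value.

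The conclusion assumes that the analyst states the rule used, limits tracking adherence to FASST over the 4 weeks, and shows the distribution of days logged beside the proportion. The data already planned allow all of this.
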